Mixed methods analyses will be used to evaluate the following three aims:

1. *To compare the effectiveness of two implementation strategies (LEAP Quality Improvement Learning Program + Academic Detailing (AD) vs. AD alone) on potentially inappropriate medication use, using a pooled analysis of effects across three trials at 18 months, two years, and three years post-baseline at the clinic-level, based on monthly assessed data from 13-36 months;*
2. *To compare the effectiveness of the two implementation strategies on secondary outcomes specific to each trial at 18 months, two years, and three years post-baseline, based on monthly assessed data from 13 to 36 months; and*
3. *To explore the effects of implementation, provider behaviors and experiences, and context, on sustained improvements in potentially inappropriate medication use.*

Methods

Clinic Randomization

Within each trial, clinics will be randomized after assenting to participate (equivalent to enrollment). Clinics will be assigned to one of two arms by a statistician, stratified further by clinic type (medical center, community clinic, or Community Living Center) if needed to ensure partial balance between arms with respect to potential confounders associated with culture and complexities associated with clinic location [1,2].

Outcomes and Analyses

As part of a pooled analysis, we will compare the same two implementation strategies across all three EBPs and take a unified approach to implementation and evaluation across the trials. Table 1 shows MIDAS measures, data collection timeframe, and data sources. While a unified dichotomous outcome, i.e., potentially inappropriate medications, was identified for each trial to allow for the pooled analysis, each trial will also be analyzed individually (see Table 1).

Table 1: MIDAS Measures showing Data Sources and Timepoints by Aim

Aim	Type	Source
Aim 1: Primary outcome		
Service Outcomes		
Proportion of potentially inappropriate care	Quantitative	CDW administrative data
Aim 2: Secondary outcomes		
Service Outcomes		
VIONE Trial		
Potentially inappropriate use of proton pump inhibitors (PPIs), aspirin, and CNS active medications (e.g., muscle relaxants), analyzed one at a time	Quantitative	CDW administrative data
Monthly medication costs for all drugs	Quantitative	CDW administrative data
Number of pharmacist medication reviews	Quantitative	CDW administrative data

Aim	Type	Source
DOAC Trial		

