Dashboard flags including potential mis-dosing, potential medication interactions, or concern for nonadherence	Quantitative	CDW administrative data
CBTI Trial		
Prevalence of any CBTI receipt	Quantitative	CBTI note templates completed by CBTI therapists
Patient Outcomes		
VIONE Trial		
Number of inappropriate medications by patient		CDW administrative data
Aim 3: Exploratory outcomes		
Employee Behavioral Outcomes		
Continuous Quality Improvement Assessment	Quantitative	LEAP and AD participants
Workgroup Cohesion & Engagement Scale	Quantitative	LEAP and AD participants
QI skill application	Quantitative	LEAP participants
Employee Experience		
Burnout	Quantitative	LEAP and AD participants
Best Places to Work	Quantitative	LEAP and AD participants
Process Evaluation		
Pragmatic Context Assessment Tool	Qualitative/ Quantitative	LEAP participants
Semi-structured interviews	Qualitative	Purposive sample of LEAP and AD participants
How often the provider uses the dashboard	Quantitative	CDW administrative data
Rates of new DOAC starts compared to warfarin starts	Quantitative	CDW administrative data
Fidelity	Qualitative/ Quantitative	Academic Detailer and Champion/LEAP Coaches
Provider satisfaction	Qualitative/ Quantitative	LEAP and AD participants
Intentions	Qualitative/ Quantitative	LEAP participants
Detailing visit documentation	Qualitative/ Quantitative	Academic Detailer and Champion
Coaching documentation	Qualitative/ Quantitative	LEAP Coaches
Semi-structured interviews	Qualitative	Purposive sample of LEAP and AD participants

Aim 1: Primary Outcomes and Pooled Analysis.

Although each trial will be conducted as an independent study, our primary aim is to compare across trials the effectiveness between the two implementation strategy arms in reducing potentially inappropriate medications during post-implementation period. To this end, we defined a unified primary outcome to allow us to combine the results *across* the three trials. The unified primary outcome will be operationalized based on a patient-level dichotomous response indicating potentially inappropriate

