Employee behavior and experience measures will be collected via five scales as listed in Table 1. Surveys will be administered via online link within invitation emails; administration will occur at baseline and 12-months post-baseline; satisfaction will be elicited at the end of each intervention (upon completion of the 6-month “core” LEAP program for LEAP team members and at the end of each AD visit for AD participants). Descriptive statistics will be generated and tests for differences across implementation strategy arms will be conducted using mixed models to account for within-clinic correlation.

Qualitative data will be collected prior to and 18-months following baseline via semi-structured interviews (virtual by telephone or conferencing software (e.g., MS Teams platform)). A purposive sample of key people (clinic leaders, supervisors, providers, and staff) at each clinic will be invited to participate so we can better understand the context in which the implementation strategies are/were deployed. The interview guides and qualitative analyses will be guided by the CFIR to identify potential and actual barriers and facilitators [6–8]. Principles embedded within the DSF will guide exploration of the degree of engagement in quality improvement and teamwork [9]. Prior to implementation, this information will help inform the work of the academic detailers and LEAP Coaches; post-

implementation, this information will help to explain quantitative findings within and across the trials. Interviews will be audio recorded and transcribed verbatim. Pre-implementation, interviews will focus on collecting practical information using a rapid analysis approach [10,11] to help tailor and adapt implementation for each participating clinic. Post-implementation, qualitative analyses will seek insights on what kinds of improvements were made, barriers and facilitators to making improvements, reflections on/satisfaction with participation in AD/LEAP and explore *relationships* between determinants, participants, and key stakeholders and how these may lead to building coalitions of support [12,13]. We will combine qualitative findings with quantitative measures from Aims 1 and 3 to help explain changes (or lack of) over time.

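### Of the five staff scales to be compared between arms in Aim 3, one has no AD-arm respondents and the other four are open to bias from respondent mix

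*Combined protocol and SAP*

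**What the plan says.** The Aims section defines the contrast as "LEAP Quality Improvement Learning Program + Academic Detailing (AD) vs. AD alone". AD is therefore delivered in both arms and LEAP in one.

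The survey paragraph of the Aim 3 section begins: "Employee behavior and experience measures will be collected via five scales as listed in Table 1". The surveys are sent at baseline and at 12 months, and "tests for differences across implementation strategy arms will be conducted using mixed models to account for within-clinic correlation". No scale is exempted from these tests, no analysis population is defined, and neither respondent role nor baseline score is named as a covariate.

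Table 1 gives LEAP participants as the only source for "QI skill application". The other four scales name both groups, for example "Continuous Quality Improvement Assessment Quantitative LEAP and AD participants" and "Workgroup Cohesion & Engagement Scale Quantitative LEAP and AD participants".

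Elsewhere the plan treats the two groups as distinct. Satisfaction is asked after the six-month core programme for "LEAP team members and at the end of each AD visit for AD participants". The process evaluation paragraph describes those whose participation is tracked as people due to be detailed, members of a LEAP team, or both.

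**The concern.** The survey paragraph plans arm comparisons on all five scales, but the data sources in Table 1 do not support that evenly. For one scale the comparator arm supplies nobody. For the other four a test can be computed, but the kinds of staff who answer may differ by arm. Randomising clinics does not protect against this, because the difference would arise from which staff are surveyed within each clinic.

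The process evaluation is meant to help explain the quantitative results, and its measures are to be combined with the Aim 1 findings. A difference in burnout, cohesion or quality-improvement scores that came from respondent mix could then be read as the way LEAP works.

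**Working it through.** **Step 1: the plan's own count.** Table 1 lists three scales under Employee Behavioral Outcomes and two under Employee Experience. 3 + 2 = 5, which matches the stated five.

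**Step 2: sources set against arms.**

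| Scale | Source in Table 1 | Who can answer in AD arm | Who can answer in LEAP+AD arm |
|---|---|---|---|
| Continuous Quality Improvement Assessment | LEAP and AD | AD participants | AD participants and LEAP team members |
| Workgroup Cohesion & Engagement | LEAP and AD | AD participants | AD participants and LEAP team members |
| QI skill application | LEAP only | nobody | LEAP team members |
| Burnout | LEAP and AD | AD participants | AD participants and LEAP team members |
| Best Places to Work | LEAP and AD | AD participants | AD participants and LEAP team members |

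**Step 3: QI skill application.** Every observation has the LEAP+AD indicator equal to 1. The indicator cannot be separated from the intercept, so no arm effect can be estimated. This needs no assumption.

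**Step 4: the other four scales.** Suppose there is no true LEAP effect. Let
- m = mean score of detailed staff, the same in both arms;
- w = share of LEAP+AD respondents who are on a LEAP team but are not detailed;
- d = pre-existing difference between those LEAP-only staff and detailed staff, in SD.

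AD-arm mean = m. LEAP+AD mean = (1 − w)m + w(m + d) = m + wd. The spurious arm difference is therefore **w × d**.

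The documents give no team composition, no overlap and no scale SDs, so w and d are assumptions:
- low end: 0.2 × 0.2 = 0.04 SD;
- high end: 0.6 × 0.5 = 0.30 SD;
- every LEAP team member also detailed and of comparable role: w = 0, so the difference is 0.

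**Step 5: what the stated model and the alternatives do.** A clinic random effect changes the standard error and the weighting of clinics. It does not change w in one arm against 0 in the other. Adding the baseline score, with slope β of the 12-month score on baseline, leaves about wd(1 − β) if d is the same at both times. That is a reduction but generally not a removal. Restricting the comparison to AD participants sets w to 0.

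**The case against.** The strongest reply is that bias in the four scales is a possibility and has not been shown. The plan's description of participants allows complete overlap between LEAP teams and detailed staff. The label naming both LEAP and AD participants may also be loose: Table 1 uses it for the interview sample, which the Aim 3 text describes as leaders, supervisors, providers and staff. This stands. A reader might infer that four of five scales are confounded, but the documents support only that they are open to it. Nor may w be taken as the share of all LEAP team members, since those who are also detailed belong to the group present in both arms.

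The gap for QI skill application reveals itself: with no AD-arm data the test cannot be run, so no wrong result can follow. That is true, and it makes the consequence small, but the text still promises a test that cannot exist.

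A reader might also infer that context cannot be studied in the AD arm, because Table 1 sources the "Pragmatic Context Assessment Tool" from LEAP participants only. The documents do not support this. Interviews about context are planned at each clinic, from a sample of both LEAP and AD participants, so only that one instrument is limited to one arm. Nor does the different timing of the satisfaction questions count against the five scales. Satisfaction and the context tool are listed under Process Evaluation, outside the five, and satisfaction after AD visits can be compared because AD is given in both arms.

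Finally, restricting the test to AD participants has its own faults. It leaves out LEAP-only staff, on whom LEAP may act most directly, and being detailed is determined after randomisation. Both criticisms stand, which is why the all-respondent comparison should be kept as a sensitivity analysis.

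**Conclusion.** One of the five planned between-arm tests cannot be estimated. This follows from Table 1 and the definition of the arms alone. The other four can be computed, but the compared population is undefined and may differ in kind between arms. The resulting bias is w × d: 0.04 to 0.30 SD over the assumed ranges, and zero with full overlap and comparable roles. The documents do not settle where in that span the trial lies.

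The changes to the analysis plan listed on the cover page do not touch this point. The scales are exploratory, Aims 1 and 2 do not depend on them, and the primary outcome is unaffected. Severity is minor.

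**What to change.** Amend the survey paragraph of the Aim 3 section in three ways:

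1. Remove QI skill application from the between-arm tests. Report it as change from baseline within the LEAP+AD arm.
2. For the other four scales, model the 12-month score on arm, with the baseline score already collected as a covariate and a clinic random effect.
3. Make the like-for-like comparison among AD participants in both arms, keeping those who also sit on LEAP teams. Report LEAP-only members descriptively, and give the all-respondent comparison as a sensitivity analysis.

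No new data are needed, provided that each person's two surveys can be linked to each other and to the participation records, which the plan does not state. The cost is a change of wording and a respondent-type filter. The price is fewer LEAP+AD respondents in the like-for-like test and no test in LEAP-only staff. Because being detailed is determined after randomisation, the write-up should call this comparison like for like in respondent type and should not present it as fully protected by randomisation.
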